## 5.2.3 Multiple imputations for response variables

Where multiple imputation is specified, the missing data will be imputed based on the individual treatment arm information.

Multiple imputation (MI) is a simulation based approach where missing values are replaced by multiple Bayesian draws from the conditional distribution of missing data given the observed data and covariates, creating multiple completed data sets.

Missing values will be imputed simultaneously based on an underlying joint normal distribution and using a Markov Chain Monte Carlo (MCMC) method.

The imputations will be done separately for each treatment group including baseline IGA, geographical region, baseline EASI score as additional covariates.

The number of imputations will be set to 100, the seed for the random function will be set to 3892203 for this study. To generate the multiple imputed data sets, the SAS procedure MI can be used as follows:

The input data set should have one record per subject with baseline EASI score and IGA score as well as the variables to be imputed (e.g. changes from baseline in EASI, or post-baseline IGA score).

Programming notes:

- The SAS procedure MIANALYZE expects a variable called "\_IMPUTATION\_" which is generated by the MI procedure. It might be needed to set the SAS option "VALIDVARNAME=UPCASE" temporarily in the program before the MI call, this option should be reset after the MIANALYZE call to VALIDVARNAME=V6.
- In case there are no missings in one treatment group, the MI procedure does not impute any values. In this case the corresponding data need to be imputed manually outside PROC MI and added to the dataset <impdata>.

The imputed data are saved in data set <impdata>. The outcomes of interest, i.e. the EASI 50/75 response and IGA 0 or 1 response will be calculated, e.g. as follows:

The treatment differences for each imputed data set will then be evaluated by Logistic regression and ODDS ratio as described in Section 5.4.2.2. This analysis will be done by \_IMPUTATION\_ for the comparison to the placebo treatment group. The model should be estimating response probability = 1 by using DESECENDING option. Using the ESTIMATE

option in the GENMOD procedure and the ODS OUTPUT data set "Estimates" provides the estimate for the odds ratio and confidence intervals.

```
PROC GENMOD <option>;
CLASS <stratum> <treatment>;
MODEL <response> = <explanatory variables> / link=logit dist=bin type3;
BY <by-variables);
ESTIMATE "OR. AIN 300 mg VS. Placebo" <treatment> 1 -1/exp;
ODS OUTPUT Estimates=Estimates;
RUN;
```

The MIANALYZE procedure expects the parameter estimate in the variables ESTIMATE, and the corresponding standard error in the variable STDERR. Measurements can be obtained from "Estimates" dataset by selecting the row with ODDS ratio estimates.

```
Data <modified dataset>;
  set Estimates;
  if substr(label,1,3)= "Exp";
  ESTIMATE=LBetaEstimate;
  STDERR=StdErr;
  effect= "OR";
  if missing(ESTIMATE) or missing(STDERR) then delete;
RUN;
```

The estimates and standard errors based on the 100 imputed data are then combined by applying Rubin's rules for multiple imputed data sets, see Little and Rubin (2002).

Programming notes:

- The variables ESTIMATE and STDERR in the input data set for the MIANALYZE procedure may not be missing. Records with missing values need to be deleted and the variable \_IMPUTATION\_ needs to be renumbered and regenerated since for each by-group the procedure expects consecutive numbers starting at 1.
- The ESTIMATE and STDERR in terms of odds ratios from logistic regressions will be transformed to follow a normal distribution before MIANALYZE procedure. They will be transformed back to Odds Ratio to get the corrected ESTIMATE and corresponding CIs.

The SAS procedure MIANALYZE will be applied as follows:

```
Step 1:
```

```
DATA <modified dataset_t>;
    SET <modified dataset>;
    estimate=log(ESTIMATE);
    stderr=(log(LBETAUPPERCL)-log(LBETALOWERCL))/(2*1.96);
RUN ;
ODS LISTING CLOSE;
ODS OUTPUT ParameterEstimates=<results> VarianceInfo=<varinfo> ModelInfo=<modelinfo>;
PROC MIANALYZE PARMS=<modified dataset>;
    BY <by-variables>;
    MODELEFFECTS OR;
RUN;
```

Novartis SAP

```
ODS LISTING;
```

```
data <results_back>;
    set <results>;
    estimate=exp(ESTIMATE);
    LCLMEAN=estimate*exp(-1.96*stderr);
    UCLMEAN=estimate*exp(+1.96*stderr);
RUN ;
```

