#### Logistic regression

Where logistic regression is specified, the binary outcome variable will be evaluated using a logistic regression model with treatment regimen, baseline IGA, geographical region (if possible).

All p-values reported on linear hypotheses about regression coefficients will be based on the Wald tests from Type III analyses. In the SAS procedure PROC GENMOD, a Type III analysis will be performed by adding the model options: TYPE3, DIST=BIN, and LINK=LOGIT. Logistic regression will be applied to response variables at each visit, and the following steps will be performed:

- 1. Run the PROC GENMOD procedure;
- 2. If convergence not reached, remove the covariates from the model one by one until convergence is reached; start with removing region, followed by baseline IGA;
- 3. If convergence not reached, perform Fisher's exact test.

It should be noted that this model might not converge if response rates are too low.

SAS code for logistic regression:

proc logistic data=aaa;

class TRT STRATA / param=glm;

Model AVAL (event='1') = TRT WEIGHT STRATA;

LSMEANS TRT / diff cl exp ilink;

run;

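### When a treatment arm has no observed responder, the SAP's handling of failed logistic fits after multiple imputation gives an invalid odds ratio for that dose

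*SAP*

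**What the plan says.** SAP 2.5.2 and 2.5.3 make logistic regression, fitted to each imputed data set and then combined, the analysis of the primary variable. The details are in the appendix:

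- **Imputation (SAP 5.2.3).** "The number of imputations will be set to 100", and "The imputations will be done separately for each treatment group".
- **Warning and fallback (SAP 5.2.2, Logistic regression).** The SAP expects trouble: "It should be noted that this model might not converge if response rates are too low". The remedy is to remove region, then baseline IGA. After that, "If convergence not reached, perform Fisher's exact test".
- **Deletion (SAP 5.2.3).** The code reads "if missing(ESTIMATE) or missing(STDERR) then delete". A programming note repeats the rule for the data set entering MIANALYZE ("Records with missing values need to be deleted") and requires the imputation index to be regenerated so that it runs consecutively from 1.
- **Standard error (SAP 5.2.3).** A later data step rebuilds it from the logs of the confidence limits: "stderr=(log(LBETAUPPERCL)-log(LBETALOWERCL))/(2*1.96").
- **Pooling (SAP 5.2.3).** "The estimates and standard errors based on the 100 imputed data are then combined" by Rubin's rules.

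The SAP sets no minimum number of retained imputations and does not ask for the number deleted to be reported.

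**The concern.** Imputation is done within each arm. If an arm has no observed responder, some completed data sets will have none either, and the maximum-likelihood odds ratio for that dose is then not finite. Whether an imputation yields a usable record therefore depends on the imputed outcome itself. Dropping such records is selection on the outcome, which Rubin's rules do not allow for, and renumbering hides how many were lost.

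The 3 mg and 10 mg arms are most exposed. They are half the size of the others, the study stopped early, and the assumed placebo response was only 10%. Any confounding therapy, and any discontinuation for adverse event or lack of efficacy, now counts as non-response (SAP 2.5.1). At stake is the validity of the model-based odds ratio for any such dose.

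**Working it through.** The plan gives no figure for this step. Its only calculation is 90% power for 360 subjects (SAP 3). That reproduces adequately: minimum power over the Protocol 9.4.2 candidate shapes is 91.6% on the logit scale at one-sided 2.5%. Only the arm sizes and the 10% placebo rate are carried forward.

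**Inputs from the SAP.** 100 imputations (5.2.3); allocation 2:1:1:2:2 and 45 planned per low-dose arm (3); 187 patients at the interim (1.1). At that ratio 187/8 ≈ 23 per low-dose arm and 2 × 187/8 ≈ 47 on placebo.

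**Assumptions.** Final arm sizes are not given, so n = 23 and n = 45 are both shown. The number *m* missing in the arm (4; range 2 to 6) and the imputed response probability *q* (5%; range 2% to 10%) are also assumed. Placebo is 5/47 or 9/90. Covariates are left out.

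**Step 1. Chance of no responder in a small arm, (1 − p)^n.**

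| True rate | n = 23 | n = 45 |
|---|---|---|
| 10% | 8.9% | 0.9% |
| 5% | 31% | 9.9% |

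**Step 2. The fit with an empty cell.** For 0/23 against 5/47 the log odds ratio runs to between −21 and −34 depending on the convergence tolerance. The standard error is 1.7 × 10^4 to 1.1 × 10^7, and the exponentiated limits are 0 and infinity. With 1/23 the fit is ordinary: log odds ratio −0.96, SE 1.13.

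**Step 3. The fallbacks.** The separation comes from the treatment term, so removing region or baseline IGA leaves it in place. Fisher's exact test supplies no log odds ratio and standard error to pool.

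**Step 4. If the failed fit becomes missing.** This happens if the Fisher fallback leaves no estimate, or if the log of a zero limit makes the standard error missing. Let k ~ Binomial(4, 0.05) be the imputed responders among 23. Without correction the odds ratio is [k/(23 − k)]/(5/42).

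| k | Probability | log OR | log OR with +0.5 in each cell |
|---|---|---|---|
| 0 | 0.8145 | none | −1.805 |
| 1 | 0.1715 | −0.963 | −0.663 |
| 2 | 0.0135 | −0.223 | −0.107 |
| 3 | 0.0005 | 0.231 | 0.277 |

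- Kept: 1 − 0.95^4 = 0.1855, about 19 of 100.
- Pooled over kept: [0.1715(−0.963) + 0.0135(−0.223) + 0.0005(0.231)]/0.1855 = −0.906, odds ratio 0.40.
- All 100 with +0.5: 0.8145(−1.805) + 0.1715(−0.663) + 0.0135(−0.107) + 0.0005(0.277) = −1.586, odds ratio 0.20.
- Inflation: exp(−0.906 + 1.586) ≈ 2.0.

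Over the ranges of *m* and *q*:

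| Arm | Kept of 100 | OR, kept only | OR, all with +0.5 |
|---|---|---|---|
| n = 23, placebo 5/47 | 4 to 47 | 0.38 to 0.46 | 0.17 to 0.30 |
| n = 45, placebo 9/90 | 4 to 47 | 0.21 to 0.25 | 0.10 to 0.17 |

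The inflation is 1.5 to 2.2 times. A simulation with normal imputation of the IGA score within the arm (40 arms per scenario) agrees: on average 3% to 36% of imputations were kept. Odds ratios were 0.39 to 0.44 against 0.17 to 0.24 at n = 23, and 0.20 to 0.25 against 0.10 to 0.15 at n = 45. In 0% to 28% of simulated arms nothing survived, so there was no odds ratio at all.

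**Step 5. If finite divergent values are kept.** Take the looser tolerance in Step 2, log odds ratio −21.4. The pooled log odds ratio is about 0.81(−21.4) + 0.19(−0.91) ≈ −17.5, with a standard error of the order of 10^4. Neither figure carries information.

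**Step 6. If placebo is the empty arm.** Every comparison is affected. Deletion then keeps only imputations with a placebo responder, so the deletion bias reverses and runs downward.

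**The case against.** The strongest counter-argument is that little depends on this odds ratio, and most of it stands.

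- **The declared summary measure bypasses the step.** For the primary and binary secondary estimands it is the difference in response rates, computed from simple rates after imputation (SAP 2.5.1, 2.6.7), with interval methods in 2.6.7 and 5.2.2. None of that uses the deleted records. What remains exposed is the pooled logistic regression that SAP 2.5.2 names as the analysis of the primary variable.
- **Upward bias is not certain.** The printed deletion test comes before the step that takes logs of the limits, and the MIANALYZE call names the data set from before that step. On that code a finite divergent fit could be kept. The programming note, applied to log-transformed input, would delete it. The SAP does not settle which happens. This makes the direction of the error uncertain but leaves no valid route.
- **The inputs may be unfavourable.** At 45 per arm and a 10% rate the chance of an empty arm is under 1%. Lack-of-efficacy and adverse-event discontinuations are not imputed. Against this, SAP 2.5.4 reports more subject-decision discontinuations than expected, and those are imputed.
- **The decision has been taken.** The trial stopped for lack of efficacy and MCP-Mod was dropped (SAP 1.1, 2.5.2, 4). Supportive estimand 3 leaves little to impute.

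A reader might also infer that whole imputed data sets are discarded. The deleted record belongs to one dose's comparison, so the other doses keep theirs.

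**Conclusion.** The point holds for the model-based odds ratio of any dose whose arm has no observed responder. The SAP's rules then lead either to pooling selected on the imputed outcome or to a divergent estimate with a meaningless interval. Under the first route the odds ratio is about 1.5 to 2.2 times the +0.5-corrected value from all 100 imputations. That value is what a Firth fit without covariates would give. The size rests on assumed arm sizes, missing counts and imputed rates. The chance of meeting the problem in a given low-dose arm is roughly 9% to 31% at 23 per arm and 0.9% to 10% at 45, for true rates of 10% to 5%.

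Two stronger readings are tempting and not supported. One is that the rule could make an ineffective low dose look effective. With placebo near 10% the inflated odds ratio stays below 1, so a deficit is understated. Passing 1 needs very low placebo response: with placebo 1/47, one imputed responder in 23 gives (1/22)/(1/46) = 2.1. The other is to read the shift in the arm's response rate as the inflation of the odds ratio. In the example that shift is 4.7% in kept imputations against 4 × 0.05/23 = 0.87% in all, about 5.4-fold. It is a ratio of arm rates, not of the odds ratios being pooled.

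The change should be made, but the point does not call the trial's conclusion into question.

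**What to change.** In SAP 5.2.3:

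1. Replace the PROC GENMOD fit in the imputation path with PROC LOGISTIC using the FIRTH option, applied to every imputed data set.
2. Pass the log odds ratios and their standard errors directly to MIANALYZE, pool all 100, and exponentiate only the pooled result. This makes the log-of-limits step unnecessary.
3. Remove the deletion and renumbering step, and the Fisher fallback within individual imputations.
4. Report the number of any fits that still fail, by comparison and visit.

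PROC LOGISTIC code already appears in SAP 5.2.2, but the imputation path is built on GENMOD output, so the extraction and pooling code must be rewritten. That is modest work. The statistical cost is slight shrinkage of odds ratios toward 1 in sparse arms.

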# 1.1 Study design

The core study (A2203) was planned as a randomized, double blind, placebo controlled, parallel group, 5-arm study in at least 360 subjects with moderate to severe Atopic Dermatitis (AD). Unbalanced randomization ratio was used, intending to result in approximately 90 subjects randomized in each of the 30 mg/day and 50 mg/day dose arms as well as in the placebo arm, and 45 subjects in each of the 3 mg/day and 10 mg/day arms. The randomization was stratified by baseline severity of atopic dermatitis (IGA score moderate or severe) and by geographical region.

The possibility to perform an interim analysis (IA) in order to support decision making concerning the current clinical study or project was addeded to the protocol in V3. This interim analysis was performed in May 2020 on 187 patients who had completed week 16 or discontinued before this timepoint. Based on the results from this IA, it was decided to stop both the core and extension studies for reasons of lack of efficacy and thus the final number of patients, and follow-up time per patient is less than planned in the protocol.

The core study (A2203) consisted of a screening period of up to 4 weeks (depending on current medication use and associated washout period), and a 16-week double blinded treatment period. The primary endpoint was to be assessed at the end of the 16 week treatment period.

After the end of treatment visit, subjects were offered the possibility of ongoing treatment in the extension study (A2203E1), or of entering the 4 week treatment-free follow up period.

[figure not shown]

The extension study (A2203E1) was intended to be a randomized, double blind, parallel group, 2-arm study in up to approximately 202 to 230 subjects. This number assumed a discontinuation rate of 15% to 25% in the core study (A2203)

In the extension study, subjects who had received ZPL389 30 mg o.d. or 50 mg o.d. doses in the core study, would continue to receive the same doses in a double-blinded fashion. Subjects who had received ZPL389 3 mg, 10 mg or placebo in the core study, would be randomized to receive ZPL389 30 mg o.d. or 50 mg o.d. in a 1:1 ratio. All subjects would receive concomitant or intermittent topical corticosteroids (TCS) and/or topical calcineurin inhibitors (TCI) along in a standardized regimen with ZPL389.

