# 2.5.3 Handling of missing values/censoring/discontinuations

Where data for IGA response are missing, either because the IGA was not recorded or because the IGA response was set to missing as part of the handling of intercurrent events, the IGA score will be imputed using multiple impuation methods and the IGA response derived from this imputed IGA score.

The multiple imputation model will include IGA categories from all visits from randomization up to Week 16.

For the estimation of the IGA response rates at Week 16 for each treatment group, each imputed dataset for subjects with missing data above will be combined with the non-missing responses for subjects without missing data. For each imputed dataset the logistic regression will be performed and results combined for estimation.

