# 2.6.7 Statistical hypothesis, model, and method of analysis

For all estimands based on binary response rates (e.g. IGA response, EASI50 response, EASI75 response) the simple response rates for each treatment group will be calculated (i.e. number of responders (after imputation as necessary) / the number of subjects in that treatment group.

Differences in response rates between ZPL389 dose groups and placebo will be calculated, and the respective 95% confidence intervals derived using a normal approximation.

For estimands based on continuous data (e.g. percentage change from baseline in EASI, approach will be used. The model will contain treatment group, baseline EASI score, geographical region if possible, baseline IGA score, visit, baseline value\*visit and treatment group\*visit as covariates, and will use an unstructured covariance matrix. Estimates of the mean responses for each visit and treatment group, and of the differences between treatment groups at week 16 will be obtained from this model, together with 95% confience intervals.

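### SAP 5.2.3: the sample pooling code reads the untransformed odds ratios and then exponentiates them, so as printed it reports exp(OR), which always exceeds 1

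*SAP*

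**What the plan says.** SAP 2.5.2 drops MCP-Mod and bases the analysis of the primary variable on the logistic regression. Section 2.5.3 adds the pooling step: "For each imputed dataset the logistic regression will be performed and results combined for estimation". Section 2.6.1 applies similar principles to EASI50 and EASI75 response.

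Section 5.2.3 holds the pooling instructions. Its programming note is correct: "The ESTIMATE and STDERR in terms of odds ratios from logistic regressions will be transformed to follow a normal distribution before MIANALYZE procedure", with a transformation back to the odds ratio afterwards. The sample code below the note opens its first step with "DATA <modified dataset_t>" and takes the logs there. The pooling call is "PROC MIANALYZE PARMS=<modified dataset>", without the `_t`. The last data step applies "estimate=exp(ESTIMATE" and builds the confidence limits from that result.

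Section 2.6.7 describes a separate quantity for binary endpoints: "Differences in response rates between ZPL389 dose groups and placebo will be calculated", with normal-approximation intervals.

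**The concern.** The note and the code in the same section disagree. The code skips the log step and keeps the back-transformation, so what it calls an odds ratio is the exponential of one. An odds ratio is positive, so that output exceeds 1 whatever the data show. A dose with no effect, or one worse than placebo, would be tabulated as favourable. The hypothesis test that PROC MIANALYZE gives by default would also be of OR = 0 instead of OR = 1. At stake are the pooled odds ratios, their confidence limits and any test taken from the pooling step, for IGA, EASI50 and EASI75 response.

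**Working it through.** The documents give no pooled odds ratio, so there is no figure to reproduce. The check traces the code and then applies it to numbers.

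**Trace (SAP 5.2.3)**

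1. `<modified dataset>` keeps only the rows of the GENMOD Estimates table whose label begins with Exp. ESTIMATE is therefore the odds ratio.
2. `<modified dataset_t>` receives log(ESTIMATE) and a log-scale standard error. No later printed line reads it.
3. PROC MIANALYZE reads `<modified dataset>`, so Rubin's rules are applied to odds ratios.
4. The final step computes exp(pooled estimate) and multiplies it by exp(±1.96 × stderr).

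**Point estimate.** As printed, the result is exp(OR): exp(0.5) = 1.65, exp(1) = 2.72, exp(2) = 7.39. Strictly, OR here is the mean of the imputation-specific odds ratios. The result does not depend on sample size.

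**Confidence limits.** Take SE(log OR) = √[1/(n₁p₁q₁) + 1/(n₀p₀q₀)] and SE(OR) = OR × SE(log OR). This assumes that the standard error in the Exp row is on the odds-ratio scale. The printed limits are exp(OR ± 1.96 × SE(OR)). The lower limit exceeds 1 whenever 1.96 × SE(log OR) < 1, that is SE(log OR) < 0.510, whatever the OR.

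Inputs: placebo IGA response of 10% and 90 per large arm (SAP 3); 187 × 2/8 ≈ 47 per large arm at the interim (SAP 1.1 and 2.12). The final arm sizes are not stated. The EASI50 rates are assumptions, because the documents give none.

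| Dose vs placebo | n per arm | SE(log OR) | Correct OR (95% CI) | As printed |
|---|---|---|---|---|
| IGA 30% vs 10% | 90 | 0.420 | 3.86 (1.69 to 8.79) | 47.3 (1.98 to 1132) |
| IGA 10% vs 10% | 90 | 0.497 | 1.00 (0.38 to 2.65) | 2.72 (1.03 to 7.20) |
| IGA 10% vs 10% | 47 | 0.688 | 1.00 (0.26 to 3.85) | 2.72 (0.71 to 10.5) |
| IGA 5% vs 10% | 90 | 0.598 | 0.47 (0.15 to 1.53) | 1.61 (0.92 to 2.80) |
| EASI50 25% vs 40% (assumed) | 47 | 0.450 | 0.50 (0.21 to 1.21) | 1.65 (1.06 to 2.56) |

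Example, last row: 0.5 − 1.96 × 0.5 × 0.450 = 0.059, and exp(0.059) = 1.06.

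**Null simulation.** Each setting had 20,000 trials with an unadjusted OR, 100 imputations drawn within arm (Jeffreys beta draws), and data missing completely at random. Trials with a zero cell were dropped. The 15% and 25% levels borrow the planning range in SAP 1.1: "This number assumed a discontinuation rate of 15% to 25% in the core study (A2203"). The table gives the share of trials whose as-printed lower limit exceeds 1.

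| Response in both arms | n | 0% missing | 15% | 25% |
|---|---|---|---|---|
| 10% | 90 vs 90 | 49.2% | 17.8% | 5.7% |
| 10% | 45 vs 90 | 3.6% | 0.4% | 0.05% |
| 10% | 47 vs 47 | 0.1% | 0% | 0% |
| 20% (assumed) | 47 vs 47 | 36% | 4.6% | 0.6% |
| 40% (assumed) | 47 vs 47 | 99.96% | 95.2% | 55.6% |
| 40% (assumed) | 23 vs 47 | 4.0% | 0% | 0% |

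Repeat runs agreed within simulation error. The printed point estimate exceeded 1 in every trial of every setting. Correct log-scale pooling put the lower limit above 1 in roughly 0.5% to 2.7% of trials.

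**The case against.** The plan states the right method in words, and the slip is one dataset name in a template that cannot run until its placeholders are replaced. A programmer who follows the note will not make the error. If it did get through, a table with every odds ratio above 1, beside some response rates below placebo, should be noticed. The declared summary measure is the difference in response rates, which this code does not touch. SAP 5.2.2 takes p-values from Type III Wald tests in GENMOD, and the SAP does not say that the default MIANALYZE test is the one reported. All of this stands, and it limits the severity.

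The false-positive rates are also fragile. With 90 per arm and 10% response, SE(log OR) is 0.497, just under the 0.510 threshold. At 47 per arm the IGA rate is close to zero, and the EASI50 rates fall sharply if response is 20% instead of 40%. The 15% to 25% missing is only a range. Discontinuations for lack of efficacy or adverse event count as non-response, which lowers it. SAP 2.5.4 reports more subject-decision discontinuations than expected, which raises it.

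None of this makes the code right. The SAP itself names two datasets and pools the wrong one, and no other pooling code is printed.

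**Conclusion.** The code is wrong as printed and contradicts the note above it. The certain consequence is an output of exp(OR) that exceeds 1 for every possible result. This follows from the code alone and needs no assumption about rates or arm sizes. The effect on confidence limits varies from almost none (IGA at 10%, 47 per arm) to most trials (EASI50 at an assumed 40%, 47 per arm, up to 15% missing). It rests on the assumed response rates, arm sizes, missingness and scale of the standard error. Pooled odds ratios, their intervals and any test read from the pooling step are affected. Response-rate differences are not. It should be fixed, but it is an error in the sample code and not in the stated method.

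**What to change.** In SAP 5.2.3, point the PARMS option at `<modified dataset_t>`, or pool the non-exponentiated log odds ratio row. Exponentiate the estimate and its limits once, after pooling.

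Clear three template leftovers in the same edit:

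- The sample contrast is labelled for another product and dose, and its 1 −1 coefficients are valid only if the BY variables subset the data to dose–placebo pairs. Otherwise write one explicit contrast of each dose (3, 10, 30 and 50 mg) against placebo.
- The treatment differences are said to be "evaluated by Logistic regression and ODDS ratio as described in Section 5.4.2.2", a section this SAP does not have. Correct the pointer.
- The sample logistic model in SAP 5.2.2 includes WEIGHT, which is not among the covariates stated there. Remove it.

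The cost is one dataset name and a few lines of clean-up, with no new data and no change to the stated method.
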